- 6) Lyft non-commercial (benzoic acid added), 10 mg/pouch
- 7) Lyft non-commercial (citric acid added), 10 mg/pouch
- 8) Lyft non-commercial (benzoic acid added, sweet base), 10 mg/pouch

Duration of treatment

Each of the study products will be used for 60 minutes for PK sampling.

Duration of subjects' involvement in the study

The screening procedure will take place up to 28 days before the start of the one 8.5 days or two 4.5 days PK sampling admission periods followed by telephone follow-up within a week after discharge from the second session. The total duration for each subject is not expected to exceed 7 weeks.

Pharmacokinetic assessments

Blood samples for pharmacokinetic parameters will be analysed at pre-dose, 5, 10, 20, 40, 50, 60, 65, 75, 90, 120, 240 and 360 minutes relative to the start of the 60 min product administration.

Safety assessments

Safety assessments will include symptom-oriented physical examination, oral mucosa examination, vital signs, clinical laboratory tests, and AE monitoring.

Statistical methods

A sample size of 32 subjects completing all PK sampling is calculated as sufficient. To achieve this, a total of 36 subject will be randomised to PK sampling.

Version 3.0

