8.6.8 Determination of sample size

8.6.8.1 Primary Analysis

Seven one-sided primary superiority comparisons (products 3 vs 2, 4 vs 3, 3 vs 6, 3 vs 7, 2 vs 5, 6 vs 7 and 8 vs 6; see Section 8.3.1 for product numbering) will be performed in this study which utilises an 8-product and 8-sequence Williams crossover design. A minimum of 32 subjects (4 subjects per sequence) will be needed to achieve a balanced design and a power of 0.848 with an alpha level of 0.00714. This will enable detecting a difference of 25% in the log scale with a correlation of 0.3 and an intrasubject CV of 0.3. A total of 36 subjects will thus be needed to be included, if an overall drop-out rate of 10% is assumed in the study.

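### The sample-size inputs in Protocol section 8.6.8.1 do not give the stated power of 0.848: either the 0.30 is not an intrasubject CV, or the power is overstated

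*Protocol*

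**What the plan says.** Protocol section 8.6.8.1 plans "Seven one-sided primary superiority comparisons" in an 8-product, 8-sequence Williams crossover. It fixes the minimum at 32 subjects, four per sequence, to "achieve a balanced design and a power of 0.848 with an alpha level of 0.00714". The assumptions behind that power are in the next sentence: "This will enable detecting a difference of 25% in the log scale with a correlation of 0.3 and an intrasubject CV of 0.3". The 36 randomised subjects follow from these 32 and a 10% drop-out rate. The synopsis carries the conclusion forward: "A sample size of 32 subjects completing all PK sampling is calculated as sufficient".

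Section 8.6.7.1.3 fixes the primary analysis. The PK parameters are ln-transformed and analysed in a mixed-effect ANOVA with treatment, period and sequence as fixed effects and subject within sequence as a random effect. With complete data, the error of any product contrast is therefore the within-subject residual variance.

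The protocol gives no source for either 0.3, and nowhere calls the CV a total or between-subject CV.

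**The concern.** There are two coherent ways to specify the variability of a within-subject comparison. One gives the within-subject (intrasubject) CV, and the variance of a log difference is then twice the within-subject log variance. The other gives the total CV of each product together with the correlation between two products in the same subject, and the correlation then removes the between-subject part. Section 8.6.8.1 takes the CV from the first and the correlation from the second. As worded, either the correlation is superfluous or the CV carries the wrong name.

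The choice matters because the variance of the difference changes by the factor one minus the correlation. The statement that 32 completers suffice rests on this figure, and so does the number randomised. Someone judging what a non-significant alginate, acid or sweet-base contrast can exclude would also look here for the power at a 25% effect.

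**Working it through.** **Inputs.** From section 8.6.8.1: N = 32 completers; seven one-sided comparisons at 0.00714 (0.05/7 = 0.007143); CV 0.30; correlation 0.3; effect 25%, first taken as a ratio of 1.25, so δ = ln 1.25 = 0.2231. From section 8.6.7.1.3: ln scale, random subject effect. On the log scale a CV of 0.30 is a variance of ln(1 + 0.30²) = ln 1.09 = 0.08618, an SD of 0.2936.

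**Method.** Noncentral t with noncentrality δ / (SD_diff / √N). Two error df are used:
- Paired t test: 32 − 1 = 31.
- Planned crossover model with complete data: 32 × 8 = 256 observations, so 255 − 7 (treatments) − 7 (periods) − 7 (sequences) − 24 (subjects within sequences) = 210.

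**Step 1. Reproducing 0.848.** Treat 0.30 as the total CV of each product, with correlation 0.3 on the original scale.
- Log-scale covariance: ln(1 + 0.3 × 0.30²) = ln 1.027 = 0.02664.
- SD_diff = √(2 × (0.08618 − 0.02664)) = 0.3451.
- Noncentrality: 0.2231 / (0.3451/√32) = 3.658.
- Power: **0.8482** with 31 df, matching the stated figure to three decimals; 0.881 with 210 df.
- Implied within-subject log variance: 0.08618 − 0.02664 = 0.05954, so the implied intrasubject CV is √(exp(0.05954) − 1) = **0.248**.

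Applying the 0.3 directly as a log-scale correlation gives 0.843 with 31 df, which is close but not exact.

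**Step 2. The inputs as labelled.** Treat 0.30 as the intrasubject CV. No correlation enters.
- SD_diff = √(2 × 0.08618) = 0.4152.
- Noncentrality: 0.2231 / (0.4152/√32) = 3.041.
- Power: **0.671** (31 df) or **0.715** (210 df).
- With all 36 subjects analysed: 0.738 (35 df) or 0.775 (238 df).
- Ratio detectable at 0.848 power with N = 32: 1.308 (31 df) or 1.293 (210 df).

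**Step 3. The other reading of the effect.** Take the 25% as δ = 0.25 log units.
- Intrasubject CV 0.30, no correlation: 0.785 (31 df) or 0.824 (210 df).
- Total CV 0.30 with correlation 0.3: 0.926 (31 df).

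Neither gives 0.848, so a ratio of 1.25 is the reading that fits.

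| Meaning of 0.30 (N = 32, one-sided 0.05/7) | Effect | 31 df | 210 df |
|---|---|---|---|
| Total CV, correlation 0.3 | ratio 1.25 | 0.848 | 0.881 |
| Intrasubject CV, no correlation | ratio 1.25 | 0.671 | 0.715 |
| Intrasubject CV, no correlation | 0.25 log units | 0.785 | 0.824 |

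All figures are for one comparison on one parameter.

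**The case against.** The strongest reply is that the calculation was sound and one word is wrong. A paired ratio test specified by a per-product CV and a correlation is a standard set-up. It needs the correlation, and it returns 0.848 exactly. On that view 0.30 was a total CV, and 0.848 is slightly conservative, since the planned model gives 0.881. This stands as a possibility. A reader might infer from section 8.6.8.1 that the within-subject gain was counted twice and that the real power is 0.67 to 0.72. The document does not support that as a fact: those figures hold only if the label is taken at face value, and nothing in the protocol shows whether the label or the power is the mistake.

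Three further points are fair:
- The Holm procedure in section 8.6.7.1.3 relaxes the threshold after the first rejection, so power at 0.00714 is the first-step figure. The same section requires both AUC and Cmax to be significant, which works the other way. The protocol states its own power at 0.00714, so that is the level at which to check it.
- If the effect is 0.25 log units and the CV is intrasubject, the shortfall is only about 2 to 6 points. That reading does not reproduce 0.848 either.
- Nothing in the protocol says that a non-significant contrast will be taken as absence of a 25% effect. That is a risk of interpretation, not a planned rule. The power figure enters no test, estimate or decision rule, and type I error is untouched.

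None of this removes the inconsistency. Nor is it a detail left to the analysis plan, because the protocol makes the calculation and states the figure itself.

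**Conclusion.** The concern holds as an inconsistency between the stated inputs and the stated power. A CV of 0.30 that is truly intrasubject does not give 0.848 at N = 32, one-sided 0.00714 and a ratio of 1.25. The size depends on what the 0.30 is:
- **Intrasubject CV:** power is 0.67 to 0.72, about 13 to 18 points below the stated figure, and the ratio detectable at 0.848 is about 1.3 rather than 1.25.
- **Total CV:** power is 0.85 to 0.88, the stated figure is right, and the real assumption is an intrasubject CV of about 0.25.

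These figures assume lognormal parameters, equal variance across products, 32 complete subjects, one comparison on one parameter, and the first-step alpha. Severity: should be fixed. The claim that 32 completers are enough rests on this sentence, but no endpoint, model, alpha or analysis set is affected.

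**What to change.** In Protocol section 8.6.8.1, go back to the original calculation, state which CV was meant, and then make one of two corrections.

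(a) If 0.30 is the intrasubject CV: keep that label, delete the correlation, and restate power as about 0.67 to 0.72 for a ratio of 1.25. Alternatively, keep 0.848 and state the detectable ratio as about 1.3. Name the error df used (31 or 210).

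(b) If 0.30 is the total CV: relabel it as *total CV 0.30, within-subject correlation 0.3 (implied intrasubject CV about 0.25)* and keep 0.848.

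In both cases write the effect as *ratio of geometric means 1.25* in place of a percentage on the log scale, and say that the power is for a single comparison on a single parameter at the first-step alpha. Under (a), the synopsis statement that 32 completers are sufficient should be aligned with the corrected figure.

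The cost is wording only; the number of subjects, the design and the analysis stay as they are. Under (a) the stated power, or the detectable effect, becomes less favourable. Under (b) only the label changes.

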8.7 Data Management

Data Management develops documentation to define activities performed during the data management conduct of the study. An EDC is the tool used to conduct all data cleaning activities, monitoring activities and review/approval activities for clinic collected data and procedure data. Data Management activities are performed in accordance with the Data Management vendor SOPs.

In addition to the cleaning activities, data entered in EDC will be checked for accuracy through quality control (QC) assessments. When the database data is declared to be complete and accurate, the database will be locked, and user access removed.

8.8 Changes in the approved study protocol

Any proposed change to the approved Final Study Protocol (including appendices) will be documented in a written and numbered protocol amendment. All amendments including substantial changes to the protocol must be submitted to appropriate IEC for approval, according to applicable national regulations. A substantial protocol amendment should be signed and dated by the same parties who signed the Final Study Protocol, as applicable.

9 ETHICS

9.1 Ethical review

Necessary approvals of the Study Protocol, the Subject Information sheet and Informed Consent form must be obtained before enrolment of any Subject into the study. Furthermore, it is the responsibility of the Sponsor to keep the Independent Ethics Committee (IEC) informed of any Suspected Unexpected Serious Adverse Reactions (SUSARs) and any substantial amendments to the protocol during the study period. The written approval from the IEC, including a study identification and the date of review will be filed at IRW and at the study site(s) together with a list of the IEC members, their titles or occupation, and their institutional affiliations. All correspondence with the IEC should be filed both at IRW and at the study site(s).

9.2 Ethical conduct of the study

The study will be performed in accordance with current revision of ICH Guidelines for Good Clinical Practice (EMA/CPMP/ICH/135/1995) last updated 15 Dec 2016 and The Declaration of Helsinki-adopted in 1964 by the 18th World Medical Assembly, in Helsinki, Finland, with later revisions.

The Declaration of Helsinki is included as Appendix 19.4 to the Protocol. Current revision of ICH Guidelines for Good Clinical Practice (CPMP/ICH/135/95) 15 Dec 2016 is referenced in Appendix 19.6.

9.3 Patient information and consent

It is the responsibility of the Investigator to give each potential study Subject adequate verbal and written information regarding the objectives and the procedures of the study as well as any risks or inconvenience involved before including the Subject in the study. The Subject must be informed about the right to withdraw from the study at any time. The Subject should be allowed sufficient time for consideration of the proposal.

Furthermore, it is the responsibility of the Investigator to obtain signed informed consent (or witnessed verbal consent, according to local regulations) from all Subjects before including them in the study. The Informed Consent form must be signed and dated before any study-specific procedures are performed, including screening procedures. The signed Informed Consent form should be filed by the Investigator for monitoring and possible future audits and/or inspections. The Investigator will confirm the receipt of the signed Informed Consent form for each Subject by documenting it to the Subject's medical chart and signing the appropriate part of the Subject's Case Report Form (CRF), if applicable.

The Final version of the Patient Information sheet and Informed Consent form is submitted to the IEC(s) and concerned Competent Authority(ie)s and must not be changed without permission from Sponsor and the local IEC.

9.4 Subject data protection

The Investigator must file a subject identification list which includes sufficient information to link records, i.e. the CRF and clinical records. This list should be preserved for possible future inspections/audits but should not be made available to the Sponsor or IRW except for monitoring or auditing purposes.

The Subjects will be informed that the data will be stored and analysed using computer, according to the regulatory requirements and local legislation for handling patient information and that identification of individual subject data will only be possible for the Investigator.

The potential study subject should be informed that by signing the Informed Consent Form he/she approves that authorised representatives from the Sponsor and IRW, the IEC and the Competent Authorities have direct access to his/her medical records for verification of clinical study procedures.

Investigators and the sponsor will preserve the confidentiality of all subjects taking part in the study, in accordance with GCP and local regulations. Subjects should be identified by a unique subject identifier** on all study documents provided to the sponsor.

11 STUDY TIMETABLE

The study is expected to start with the first screening visit in Q1 2020 and to be completed in Q2/Q3 2020.

12 DISCONTINUATION OF THE STUDY

The sponsor or its representative may terminate the study at any time for scientific or corporate reasons.

If the study is prematurely terminated or suspended for any reason, the clinical site or an investigator (or delegate) should promptly inform the study subjects, should assure appropriate therapy and follow-up for the subjects and should inform the IEC when required.

13 FINAL STUDY REPORT AND PUBLICATION OF STUDY RESULTS

The CRO will prepare a clinical study report (CSR). The report will be written in accordance with the International Conference on Harmonisation (ICH). Note for Guidance on Structure and content of CSRs.

The draft report may be submitted for Quality Assurance audit, the findings of which will be incorporated in the final version.

All data collected during the study will be the property of the Sponsor.

The publication policy for this study will be part of a separate agreement between the Investigator and the Sponsor.

14 RECORD RETENTION

The Investigator must arrange for retention at the investigational site of a list of the subjects and their identifying code, subject files and other study documents including all essential documents. The archiving period must be adapted to regulations in force and should not be shorter than ten years after the termination of the study and the presentation of the final report.

It is the responsibility of the Sponsor to inform the investigator/institution as to when these documents no longer need to be retained

16 INSURANCE/INDEMNITY

The Investigator agrees to notify the Sponsor BAT and the CRO whenever he/she becomes aware of a claim or action, and to co-operate with and to authorise the Sponsor BAT to carry out sole management of such claim or action.

The Sponsor's responsibility there under is covered by insurance. The insurance also covers the Sponsor's liability under law and generally accepted liability standards within the pharmaceutical industry towards any third parties, including subjects, as Sponsor of the study.

It is the sponsor's responsibility to guarantee sufficient insurance coverage should any serious events or deaths result, either directly or indirectly, from the execution of the present protocol.

17 STUDY AGREEMENTS

The Principal Investigator at the investigational site must comply with all the terms, conditions, and obligations of the Clinical Trial Agreement (CTA) for this study.

A separate Financial Agreement between Sponsor and the Principal Investigator and/or institution will be filed in the Investigator Site File and the Trial Master File.

19.2 Clinical Laboratory Evaluations

19.3 Product Subjective Measures Questionnaires

Subject number: _____

Date of completion: ____ / ___ / 20____

Product: _____

Product Liking Questionnaire (PLQ)

At this moment, how much do you like the product?

0	1	2	3	4	5	6	7	8	9	10
Strongly					Neither					Strongly
dislike					like nor					like
					dislike					

Overall Intent to Use Again (OIUA) Questionnaire

Rate the degree to which you would like to use the product again.

0	1	2	3	4	5	6	7	8	9	10
Not at all										Very
										much

19.4 Declaration of Helsinki

Adopted by the 18th WMA General Assembly, Helsinki, Finland, June 1964 and amended by the:

29th WMA General Assembly, Tokyo, Japan, October 1975

35th WMA General Assembly, Venice, Italy, October 1983

41st WMA General Assembly, Hong Kong, September 1989

48th WMA General Assembly, Somerset West, Republic of South Africa, October 1996

52nd WMA General Assembly, Edinburgh, Scotland, October 2000

53rd WMA General Assembly, Washington DC, USA, October 2002 (Note of Clarification added)

55th WMA General Assembly, Tokyo, Japan, October 2004 (Note of Clarification added) 59th WMA General Assembly, Seoul, Republic of Korea, October 2008 64th WMA General Assembly, Fortaleza, Brazil, October 2013

Preamble

1. The World Medical Association (WMA) has developed the Declaration of Helsinki as a statement of ethical principles for medical research involving human subjects, including research on identifiable human material and data.

The Declaration is intended to be read as a whole and each of its constituent paragraphs should be applied with consideration of all other relevant paragraphs.

2. Consistent with the mandate of the WMA, the Declaration is addressed primarily to physicians. The WMA encourages others who are involved in medical research involving human subjects to adopt these principles.

General Principles

3. The Declaration of Geneva of the WMA binds the physician with the words, "The health of my patient will be my first consideration," and the International Code of Medical Ethics declares that, "A physician shall act in the patient's best interest when providing medical care."

4. It is the duty of the physician to promote and safeguard the health, well-being and rights of patients, including those who are involved in medical research. The physician's knowledge and conscience are dedicated to the fulfilment of this duty.

5. Medical progress is based on research that ultimately must include studies involving human subjects.

6. The primary purpose of medical research involving human subjects is to understand the causes, development and effects of diseases and improve preventive, diagnostic and therapeutic interventions (methods, procedures and treatments). Even the best proven interventions must be evaluated continually through research for their safety, effectiveness, efficiency, accessibility and quality.

7. Medical research is subject to ethical standards that promote and ensure respect for all human subjects and protect their health and rights.

8. While the primary purpose of medical research is to generate new knowledge, this goal can never take precedence over the rights and interests of individual research subjects.

9. It is the duty of physicians who are involved in medical research to protect the life, health, dignity, integrity, right to self-determination, privacy, and confidentiality of personal information of research subjects. The responsibility for the protection of research subjects must always rest with the physician or other health care professionals and never with the research subjects, even though they have given consent.

10. Physicians must consider the ethical, legal and regulatory norms and standards for research involving human subjects in their own countries as well as applicable international norms and standards. No national or international ethical, legal or regulatory requirement should reduce or eliminate any of the protections for research subjects set forth in this Declaration.

11. Medical research should be conducted in a manner that minimises possible harm to the environment.

12. Medical research involving human subjects must be conducted only by individuals with the appropriate ethics and scientific education, training and qualifications. Research on patients or healthy volunteers requires the supervision of a competent and appropriately qualified physician or other health care professional.

13. Groups that are underrepresented in medical research should be provided appropriate access to participation in research.

14. Physicians who combine medical research with medical care should involve their patients in research only to the extent that this is justified by its potential preventive, diagnostic or therapeutic value and if the physician has good reason to believe that participation in the research study will not adversely affect the health of the patients who serve as research subjects.

15. Appropriate compensation and treatment for subjects who are harmed as a result of participating in research must be ensured.

Risks, Burdens and Benefits

16. In medical practice and in medical research, most interventions involve risks and burdens.

Medical research involving human subjects may only be conducted if the importance of the objective outweighs the risks and burdens to the research subjects.

17. All medical research involving human subjects must be preceded by careful assessment of predictable risks and burdens to the individuals and groups involved in the research in comparison with foreseeable benefits to them and to other individuals or groups affected by the condition under investigation.

Measures to minimise the risks must be implemented. The risks must be continuously monitored, assessed and documented by the researcher.

18. Physicians may not be involved in a research study involving human subjects unless they are confident that the risks have been adequately assessed and can be satisfactorily managed.

When the risks are found to outweigh the potential benefits or when there is conclusive proof of definitive outcomes, physicians must assess whether to continue, modify or immediately stop the study.

Vulnerable Groups and Individuals

19. Some groups and individuals are particularly vulnerable and may have an increased likelihood of being wronged or of incurring additional harm.

All vulnerable groups and individuals should receive specifically considered protection. 20. Medical research with a vulnerable group is only justified if the research is

responsive to the health needs or priorities of this group and the research cannot be carried out in a non-vulnerable group. In addition, this group should stand to benefit from the knowledge, practices or interventions that result from the research. Scientific Requirements and Research Protocols

21. Medical research involving human subjects must conform to generally accepted scientific principles, be based on a thorough knowledge of the scientific literature, other relevant sources of information, and adequate laboratory and, as appropriate, animal experimentation. The welfare of animals used for research must be respected.

22. The design and performance of each research study involving human subjects must be clearly described and justified in a research protocol.

The protocol should contain a statement of the ethical considerations involved and should indicate how the principles in this Declaration have been addressed. The protocol should include information regarding funding, sponsors, institutional affiliations, potential conflicts of interest, incentives for subjects and information regarding provisions for treating and/or compensating subjects who are harmed as a consequence of participation in the research study.

In clinical trials, the protocol must also describe appropriate arrangements for post-trial provisions.

Research Ethics Committees

23. The research protocol must be submitted for consideration, comment, guidance and approval to the concerned research ethics committee before the study begins. This committee must be transparent in its functioning, must be independent of the researcher, the sponsor and any other undue influence and must be duly qualified. It must take into consideration the laws and regulations of the country or countries in which the research is to be performed as well as applicable international norms and standards but these must not be allowed to reduce or eliminate any of the protections for research subjects set forth in this Declaration.

The committee must have the right to monitor ongoing studies. The researcher must provide monitoring information to the committee, especially information about any serious adverse events. No amendment to the protocol may be made without consideration and approval by the committee. After the end of the study, the researchers must submit a final report to the committee containing a summary of the study's findings and conclusions.

Privacy and Confidentiality

24. Every precaution must be taken to protect the privacy of research subjects and the confidentiality of their personal information.

Informed Consent

25. Participation by individuals capable of giving informed consent as subjects in medical research must be voluntary. Although it may be appropriate to consult family members or community leaders, no individual capable of giving informed consent may be enrolled in a research study unless he or she freely agrees.

26. In medical research involving human subjects capable of giving informed consent, each potential subject must be adequately informed of the aims, methods, sources of funding, any possible conflicts of interest, institutional affiliations of the researcher, the anticipated benefits and potential risks of the study and the discomfort it may entail, post-study provisions and any other relevant aspects of the study. The potential subject must be informed of the right to refuse to participate in the study or to withdraw consent to participate at any time without reprisal. Special attention should be given to the specific information needs of individual potential subjects as well as to the methods used to deliver the information.

After ensuring that the potential subject has understood the information, the physician or another appropriately qualified individual must then seek the potential subject's freely given informed consent, preferably in writing. If the consent cannot be expressed in writing, the non-written consent must be formally documented and witnessed. All medical research subjects should be given the option of being informed about the general outcome and results of the study.

27. When seeking informed consent for participation in a research study the physician must be particularly cautious if the potential subject is in a dependent relationship with the physician or may consent under duress. In such situations the informed consent must

be sought by an appropriately qualified individual who is completely independent of this relationship.

28. For a potential research subject who is incapable of giving informed consent, the physician must seek informed consent from the legally authorised representative. These individuals must not be included in a research study that has no likelihood of benefit for them unless it is intended to promote the health of the group represented by the potential subject, the research cannot instead be performed with persons capable of providing informed consent, and the research entails only minimal risk and minimal burden.

29. When a potential research subject who is deemed incapable of giving informed consent is able to give assent to decisions about participation in research, the physician must seek that assent in addition to the consent of the legally authorised representative. The potential subject's dissent should be respected.

30. Research involving subjects who are physically or mentally incapable of giving consent, for example, unconscious patients, may be done only if the physical or mental condition that prevents giving informed consent is a necessary characteristic of the research group. In such circumstances the physician must seek informed consent from the legally authorised representative. If no such representative is available and if the research cannot be delayed, the study may proceed without informed consent provided that the specific reasons for involving subjects with a condition that renders them unable to give informed consent have been stated in the research protocol and the study has been approved by a research ethics committee. Consent to remain in the research must be obtained as soon as possible from the subject or a legally authorised representative.

31. The physician must fully inform the patient which aspects of their care are related to the research. The refusal of a patient to participate in a study or the patient's decision to withdraw from the study must never adversely affect the patient-physician relationship.32. For medical research using identifiable human material or data, such as research on material or data contained in biobanks or similar repositories, physicians must seek informed consent for its collection, storage and/or reuse. There may be exceptional situations where consent would be impossible or impracticable to obtain for such

research. In such situations the research may be done only after consideration and approval of a research ethics committee.

Use of Placebo

33. The benefits, risks, burdens and effectiveness of a new intervention must be tested against those of the best proven intervention(s), except in the following circumstances:

Where no proven intervention exists, the use of placebo, or no intervention, is acceptable; or

Where for compelling and scientifically sound methodological reasons the use of any intervention less effective than the best proven one, the use of placebo, or no intervention is necessary to determine the efficacy or safety of an intervention and the patients who receive any intervention less effective than the best proven one, placebo, or no intervention will not be subject to additional risks of serious or irreversible harm as a result of not receiving the best proven intervention.

Extreme care must be taken to avoid abuse of this option.

Post-Trial Provisions

34. In advance of a clinical trial, sponsors, researchers and host country governments should make provisions for post-trial access for all participants who still need an intervention identified as beneficial in the trial. This information must also be disclosed to participants during the informed consent process.

Research Registration and Publication and Dissemination of Results

35. Every research study involving human subjects must be registered in a publicly accessible database before recruitment of the first subject.

36. Researchers, authors, sponsors, editors and publishers all have ethical obligations with regard to the publication and dissemination of the results of research. Researchers have a duty to make publicly available the results of their research on human subjects and are accountable for the completeness and accuracy of their reports. All parties should adhere to accepted guidelines for ethical reporting. Negative and inconclusive as well as positive results must be published or otherwise made publicly available. Sources of funding, institutional affiliations and conflicts of interest must be declared in the publication. Reports of research not in accordance with the principles of this Declaration should not be accepted for publication.

Unproven Interventions in Clinical Practice

37. In the treatment of an individual patient, where proven interventions do not exist or other known interventions have been ineffective, the physician, after seeking expert advice, with informed consent from the patient or a legally authorised representative, may use an unproven intervention if in the physician's judgement it offers hope of saving life, re-establishing health or alleviating suffering. This intervention should subsequently be made the object of research, designed to evaluate its safety and efficacy. In all cases, new information must be recorded and, where appropriate, made publicly available.

